1. INTRODUCTION/ REVIEW ”

Urolithiasis is a commonly occurring pathologic condition of the urinary tract which urologists worldwide are dealing with on daily basis specially with increasing incidence in the last years with the majority of them at upper urinary tract¹.

Upper ureteric stones specially with large size are not likely to pass spontaneously having a chance of 22% versus distal ureteric stones which have a chance of 71% of spontaneous passage². An exact cut-off size for stones that are likely to pass spontaneously cannot be provided; < 10 mm may be considered a best estimate³. Impacted stones irrespective of size won't pass spontaneously defined radiologically by non movable stone down the ureter on computerized tomography scan for 1 month or inability to pass a guidewire beyond the stone intraoperatively⁴. Upper ureteric stones have been considered a matter of controversy when addressing the most convenient interventional procedure for their treatment taking in consideration the variety of interventional options within the armamentarium of contemporary urology. These options include retrograde URSL, SWL, antegrade URSL and ureterolithotomy, laparoscopic or open, in certain cases⁵.

The European Association of Urology (EAU) and American Association of Urology (AUA) guidelines on urolithiasis recommended use of URSL and SWL for treating upper ureteric stones^{5,6}. In the recent years there has been a paradigm shift towards increased use of URSL with decreased SWL use for treating upper urinary tract stones^{7,8}. It has been postulated that URSL for ureteric stones has higher stone free rate compared to SWL with less need for secondary procedures⁹. Also URSL has a more favorable cost-efficiency profile compared to SWL in treating proximal ureteric stones when chosen as the primary treatment modality¹⁰. The EAU guidelines on urolithiasis recommends URSL as first option to treat proximal ureteric stones > 10 mm in maximum dimension and to use antegrade access whenever the collecting system is dilated or the retrograde access is inconvenient⁵. Recently many studies assessed the antegrade access for upper ureteric stones making use of different urological endoscopes available with different percutaneous tract sizes through the kidney according to used endoscope varying between conventional nephroscopes¹¹, semirigid ureteroscopes¹¹, mini nephroscopes¹², flexible nephroscopes¹³ and flexible ureteroscopes⁴ demonstrating superior stone free rate with percutaneous antegrade access with comparable safety profile with retrograde URSL.

2. AIM/ OBJECTIVES (Maximum 300 words)

We aim to assess the efficacy and safety of antegrade URSL in treating upper ureteric stones >10 mm in its maximum dimension and impacted upper ureteric stones irrespective of its size in comparison to retrograde URSL and evaluate feasibility, adverse events, hospital stay and cost benefit of both techniques.

3. METHODOLOGY:

Patients and Methods/ Subjects and Methods/ Material and Methods (Maximum 1000 words)

“References may be needed”

- **Type of Study**

Randomized prospective study

- **Study Setting**

- Department of urology, Ain Shams University

- **Study Period**

- 4 years

- **Study Population**

- Inclusion Criteria:

- Age > 18 years

- Upper ureteric stones > 10 mm

- Impacted upper ureteric stones defined by non movable stone on CTUT for 1 month or intraoperative failure to pass a guidewire beyond the stone

- Exclusion Criteria:

- Unresolved urinary tract infection

- Uncorrected coagulopathy

- pregnancy

- Anatomical abnormalities of the urinary system as horse shoe kidney, pelvic ectopic kidney and ureteric strictures.

- Severe orthopedic malformation hindering prone position or antegrade ureteric access as Kyphosis, scoliosis.

- Pediatric age groups < 18 years

- Ureteric Stent in place

- Concurrent renal stones
- Bladder cancer, upper urothelial tumors and renal tumors.

- **Sampling Method**

Randomization will be done by statistician.

- **Sample Size**

50 patients in either arm, aborted cases will be included.

- **Ethical Considerations**

Patients will be asked to provide a signed written informed consent

- **Study Procedures:**

- **Pre operative work up:**

- Patients will undergo detailed history taking, physical examination.

- **Laboratory work-up:**

- Complete blood count (CBC)
- Coagulation profile
- Kidney function tests
- Liver function tests
- Urine analysis
- Urine culture and sensitivity

- **Imaging:**

- Patients will undergo plain computed tomography of the urinary tract (CTUT) to be eligible for diagnosis of upper ureteric stone. Upper ureteric stone definition will be the distance from pelviureteric junction to

the proximal border of sacroiliac junction. Impacted stones will be defined as non movable stones for 1 month on CTUT

- Signed informed consent

- Patients who fulfill inclusion criteria will be randomized into 2 groups:
Antegrade URSL(A-group), retrograde URSL(B-group).

- Operative procedure:

Antegrade URSL- Group A:

- 1- All patients will be anesthetized by general anesthesia.
- 2- The patient will be in lithotomy position, cystoscopy will be done, guide wire will be passed to the ureter to bypass the ureteric stone and advanced to the collecting system of the kidney, ureteric catheter (6 Fr, open tip) will pass over the guidewire and an indwelling urethral catheter will be placed in the urinary bladder
- 3- The patient will be placed in prone position, retrograde pyelography via ureteric catheter will be done, puncture of the collecting system will be done through upper or middle calyx using 18-gauge percutaneous puncture needle guided by fluoroscopy. In case of impacted stones and non passage of guidewire beyond the stone, localization of renal pelvis by 18 gauge Shiba needle in prone position guided by ultrasound will be done then antegrade pyelography will be performed to proceed with calyceal puncture.
- 4- 0.035 inch PTFE J tip guidewire will be introduced through the puncture needle sheath and negotiated into the ureter down to the stone guided by fluoroscopy.
- 5- Dilatation of the percutaneous tract using Amplatz dilator 14 fr and its sheath guided by fluoroscopy.
- 6- Withdrawing ureteric catheter after passage of 0.035 inch PTFE straight guide wire through it to the kidney to act as safety wire guided by fluoroscopy.
- 7- Passage of Ureteral access sheath 10-12 fr or the Flexible URS itself (Richard Wolf, Boa Vision) on the J tip guidewire then the guidewire will be withdrawn
- 8- Stone dusting using 200 micron Laser fiber and Lumenis Pulse 50H Laser machine utilizing Holmium Laser
- 9- Antegrade ureterography via the ureterosocpe will be done at end of stone dusting

10- Passage of 0.035 PTFE straight tip (Boston Scientific) guidewire through the URS to the bladder guided by Fluoroscopy then the safety guidewire will be withdrawn retrogradely

11- Ureteroscope will be withdrawn with ureteral access sheath, if used, along with inspection of ureter up to the kidney

12- Antegrade JJ stent 6fr/26 will be passed antegradely over the straight guidewire to the bladder

13- Amplatz sheath will be pulled out and puncture site closed with a deep mattress suture

- Retrograde URS- Group B:

- 1- All patients will be anesthetized by general anesthesia.
- 2- Patients will be placed in supine position
- 3- Cystoscopy and passage of 0.035-inch straight tip guidewire in the ureter up to the kidney guided by fluoroscopy.
- 4- 10 Fr dual lumen ureteric catheter is passed along guidewire guided by fluoroscopy to pass a second safety guide wire then ureteric dilatation by Teflon dilators up to 14 Fr then passage of ureteral access sheath 12-14 Fr or the Flexible URS itself ,if the ureter cannot be dilated, on one of the 2 guidewires guided by fluoroscopy then the guidewire will be withdrawn
- 5- When using flexible ureteroscope, 200 micron Laser fiber will be used to complete stone dusting
- 6- Retrograde pyelography will be performed at end of procedure then 6fr/26cm JJ stent will be fixed

- Post operative:

- In both groups, urethral catheter will be removed after full recovery from anesthesia and blood sample will be obtained on the morning of day 1 post operative for CBC and then patient will be discharged.
- Patients will undergo CTUT after 3 weeks to confirm stone free state before JJ stent removal, stone free state will be defined as no or 2-3 mm stone fragments on CTUT

- **Data collection and deposition:** Data will be collected and deposited in both urology departments.

We used the Statistical Package for Social Sciences (IBM Corp. Released 2019. IBM SPSS Statistics for Windows, Version 29.0. Armonk, NY: IBM Corp.) for data analysis. Descriptive statistics were presented as mean \pm standard deviation (SD) or as numbers and percentages. Normality was tested using the Shapiro-Wilk test. Data that were normally distributed were presented as mean \pm SD, while non-normally distributed data were presented as median and 95% confidence intervals (CIs).

The chi-square (χ^2) test assessed relationships between categorical variables. For parametric variables, the student's t-test was applied to compare means between study groups, while the Mann-Whitney U test was used to compare medians for variables such as stone size and hospital stay. Fisher's exact test was employed for categorical variables with expected counts < 5 . Spearman's correlation was used to analyze relationships between non-normally distributed variables. Binary logistic regression was done to illustrate the odds ratio for complications. A P-value < 0.05 was considered statistically significant.

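### Cheap improvement, not an error: add one stone-free risk difference adjusted for pre-operative CT stone size, and for CT-documented impaction as far as it is recorded

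*Combined protocol and SAP*

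**What the plan says.** The only efficacy measure the plan defines is on the 3-week CT (Methodology, Post operative): "stone free state will be defined as no or 2-3 mm stone fragments on CTUT".

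The Statistical analysis section does not name a test for it. The chi-square "test assessed relationships between categorical variables", with Fisher's exact test where expected counts are small. Stone-free status would presumably fall there, but that is an inference. Stone size is mentioned once, as something to compare between groups: "the Mann-Whitney U test was used to compare medians for variables such as stone size and hospital stay". The only model is described as follows: "Binary logistic regression was done to illustrate the odds ratio for complications". Its covariates are not listed.

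The Aim covers "upper ureteric stones >10 mm" and also impacted stones of any size, so both features vary between patients. Impaction has two definitions. Under Imaging: "Impacted stones will be defined as non movable stones for 1 month on CTUT". The Inclusion Criteria add an alternative: "or intraoperative failure to pass a guidewire beyond the stone". The imaging work-up reads: "Patients will undergo plain computed tomography of the urinary tract (CTUT) to be eligible for diagnosis of upper ureteric stone". Sample size is 50 per arm. Randomisation is assigned to a statistician, and no stratification is described.

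**The concern.** If large or impacted stones clear less often, a chance excess of them in one arm moves that trial's observed stone-free difference. The documents do not quantify any such effect. No stratification is described that would limit the imbalance, and no described analysis corrects for it. A Mann-Whitney comparison of stone size can show an imbalance but does not remove its effect on the stone-free result.

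At stake is how far a reader can trust one trial's point estimate. The long-run validity of the test is not in question. If an adjusted estimate agrees with the unadjusted one, the recorded factors did not drive the result. If they differ, the reader needs to know.

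**Working it through.** **Inputs from the documents.** 50 per arm; significance at P < 0.05 (two-sided assumed); binary stone-free outcome; no stratification described. No power, rates or effect size are given, so the plan has no figure to reproduce here.

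**Assumed inputs.** Overall stone-free 83%; stone size SD 3.12 mm (median 13 mm); size odds ratio 1.0 to 1.2 per mm; impaction odds ratio 2.5 or 4; 30% or 50% impacted.

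**1. Imbalance in stone size.**
- SE of the difference in means: 3.12 × √(2/50) = 0.624 mm.
- P(at least 1 mm, either direction): 1/0.624 = 1.60, so P = 0.109.
- Mean imbalance in those trials: 1.26 mm.
- Effect per mm on the risk scale, about p(1 − p) × ln(OR): 0.83 × 0.17 × ln 1.1 = 1.34 points; 0.83 × 0.17 × ln 1.2 = 2.57 points.
- Shift: 1.26 × 1.34 ≈ 1.7 points; 1.26 × 2.57 ≈ 3.3 points (3.25 before rounding).

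Size can be measured on the CT that every patient has, so adjustment can address this part in all patients.

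**2. Imbalance in impaction.** From two independent Binomial(50, p) counts, P(difference of at least 8 patients, 16 points) is 0.101 at 30% impacted and 0.133 at 50%. The mean imbalance in those trials is about 19 points. With stone-free 90% in non-impacted and 78% in impacted stones, the shift is about 0.19 × 12 = 2.3 points. With 69% in impacted stones it is about 0.19 × 21 = 4.0 points.

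**3. Effect of incomplete CT documentation.** A linear regression on arm and a yes/no impaction term gives the same point estimate as a Mantel-Haenszel risk difference, so simulated results for the latter apply (300,000 trials per scenario):

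| Impacted stones documented on CT | Share of the impaction shift that remains |
|---|---|
| 100% | about 0 |
| 75% | 33–41% |
| 50% | 60–68% |
| 25% | 82–87% |

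**4. Precision and power with both factors.**
- If neither factor is prognostic, the approximate inflation for q = 2 uninformative covariates and n = 100 is q/(n − q − 3) = 2/95 = 2.1%. Simulation agrees, at about 2%.
- With impaction odds ratios of 2.5 or 4 and size odds ratios of 1.0 to 1.2 per mm, the change runs from a 1% loss to a 9% saving.
- The whole range is therefore about −2% to +9%.
- For a 20-point difference, power was 64–66% for the chi-square and 63–68% for the linear model, a change of about −2.5 to +3 points. Type I error was 5.1–5.8% and 4.2–4.8% respectively, so part of the power difference reflects test size and not adjustment.

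**5. Day-1 haemoglobin (secondary).** With equal SDs at both times and correlation r, ANCOVA variance is lower than that of a change score by 1 − (1 + r)/2, and lower than that of day-1 values alone by r². At an assumed r of 0.6 to 0.9 these are 20% to 5%, and 36% to 81%.

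**The case against.** The strongest case against is that this is a preference with little return. On impaction alone, at 50% CT documentation, the variance saved is 0.1–0.4% (1.5–2.4% with the larger clearance gap) and power changes by −0.4 to +0.4 points. All inputs are assumed. This stands as regards precision and power, and the point does not rest on them.

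Other objections that stand in part:

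- **Too many estimates.** Separate stratified, linear and penalised logistic results would widen the room for selective reporting, especially as the Statistical analysis section is written in the past tense and no primary outcome is designated. Hence a single added estimate.
- **CT impaction may not be on file.** One-month immobility needs imaging over time, stones above 10 mm qualify without it, and the work-up describes one plain CT. Only size is reliably available, so size is the base covariate.
- **Size and impaction are linked by eligibility.** Under the Aim, stones of 10 mm or less enter only if impacted. In one illustrative case (40% impacted, 40% of those at 10 mm or less, odds ratios 2.5 and 1.1 per mm) the saving fell from 2.8% to 1.4%, and to about −0.1% at 50% documentation. These values lie inside the range above and do not change the conclusion.
- **Haemoglobin is a side issue.** No such comparison is named, so that advice is conditional.

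A reader might also infer that the unadjusted test is biased or invalid. It is not: over all randomised trials the simulated type I error of the chi-square was 5.1–5.5%, and 5.5% even when impaction had no effect, so the small excess does not come from omitting the covariate. Nor do the documents show that size or impaction affects clearance, or that chi-square is the designated stone-free test.

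**Conclusion.** The point holds as an optional improvement. No stone-free estimate adjusted for CT stone size or impaction is described, although these define eligibility and no stratification is described. The benefit is partial removal of chance imbalance: about 1.7 to 3.3 points in the roughly 11% of trials with a size imbalance of at least 1 mm, plus whatever part of an impaction imbalance the CT record captures. Unrecorded impaction and unmeasured factors remain unadjusted. The effect on variance is between a 2% loss and a 9% saving.

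These sizes rest wholly on assumed rates, spreads and odds ratios. What rests on the documents is the absence of the adjusted estimate, the two eligibility routes, the two definitions of impaction, and the order of randomisation before surgery.

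**What to change.** Keep the unadjusted stone-free comparison as the main result and say so explicitly. Add one sensitivity estimate: the risk difference with 95% CI from a linear regression of stone-free (0/1) on arm and pre-operative CT stone size in mm, with HC3 standard errors. Add CT-documented impaction (yes, against no or not documented) only as far as it is recorded, and report how many patients have it documented. No further stratified or logistic stone-free estimates are needed.

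Do not use intraoperative guidewire failure as a covariate or stratum. As the plan is ordered it is seen at surgery, after randomisation, and is not a baseline factor.

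If the data are already analysed, label the estimate post hoc. If day-1 haemoglobin is compared between arms, use ANCOVA on the pre-operative CBC value in place of a t-test on day-1 or change values.

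Cost: minor analysis work, with no added patients or visits. Documenting impaction may require retrieving earlier scans. The downsides are a second stone-free estimate to report and a possible slight loss of precision.

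### For hospital stay, the Mann-Whitney test is described as a comparison of medians; it can be significant with identical medians, and no between-arm estimate is planned to show what differs

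*Combined protocol and SAP*

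**What the plan says.** The Statistical analysis section at the end of the document states that "the Mann-Whitney U test was used to compare medians for variables such as stone size and hospital stay". The significance rule is "A P-value < 0.05 was considered statistically significant"; sidedness is not given. Non-normal data are to be summarised by a median with a 95% CI. The section makes no equal-shape or pure-shift assumption and names no between-arm effect measure for these variables.

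Three other places bear on the point:

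- Aim/Objectives lists hospital stay among several things to assess: "evaluate feasibility, adverse events, hospital stay and cost benefit of both techniques". No outcome is designated primary.
- Sample Size gives "50 patients in either arm, aborted cases will be included".
- The Post operative part of the Methodology gives both groups the same instruction: "blood sample will be obtained on the morning of day 1 post operative for CBC and then patient will be discharged".

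**The concern.** The Mann-Whitney statistic estimates θ = P(A > B) + ½P(A = B), the probability that a patient in one arm has the larger value, with ties counted as half. Its reference distribution assumes that the two arms have the same whole distribution. A rejection can be read as a difference in medians only if the arms differ by a shift of one common shape.

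Hospital stay may well not follow that pattern. With one discharge instruction for both arms, many stays are likely to tie at about one day. An effect of route, for example through complications, could then lie wholly in the minority kept longer, with both medians at one day.

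What is at stake is the interpretation of one stated objective. The P-value would answer one question and the medians printed beside it another. Nothing in the plan would tell the reader how much longer patients stay, or how many stay longer.

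**Working it through.** **Inputs.** From the documents: 50 per arm and a 0.05 threshold, taken as two-sided. The documents give no distribution of stay, unit of stay, effect size or power calculation, so there is no planned figure to reproduce. Every stay distribution below is an assumption.

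**Whole-day model.** A patient stays 1 day with probability 1 − p, otherwise 1 day plus 1 + Poisson(0.7) extra days. Since p < 0.5 in both arms, both true medians are 1 day. The extra days have the same distribution in both arms, so:

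- θ = 0.5 + (p₂ − p₁)/2. For 10% v 25%: 0.25×0.90 + ½(0.75×0.90) + ½(0.25×0.10) = 0.225 + 0.3375 + 0.0125 = 0.575.
- Difference in mean stay = (1 + 0.7)(p₂ − p₁). For 10% v 25%: 1.7×0.15 = 0.255 day.

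Rejection rates come from 6,000 simulated trials per row with the tie-corrected normal approximation (Monte Carlo standard error at most √(0.25/6000) ≈ 0.006).

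| Kept beyond day 1 | True medians (days) | θ | Mean difference (days) | Mann-Whitney rejects |
|---|---|---|---|---|
| 10% v 10% | 1 v 1 | 0.500 | 0 | 0.052 |
| 10% v 25% | 1 v 1 | 0.575 | 0.255 | 0.504 |
| 5% v 20% | 1 v 1 | 0.575 | 0.255 | 0.641 |
| 10% v 30% | 1 v 1 | 0.600 | 0.340 | 0.720 |

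Repeat runs of the last three rows gave 0.50-0.52, 0.64-0.66 and 0.71-0.72. In these scenarios over 99% of the significant trials had identical sample medians.

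**A second set of shapes.** Percentages staying 1/2/3 days, 20,000 trials each, both true medians 1 day:

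- 70/20/10 in both arms: rejects 4.7%
- 60/25/15 v 70/20/10: 20%
- 70/20/10 v 80/15/5: 22%
- 65/25/10 v 85/10/5: 62%
- 60/25/15 v 90/8/2: 96%

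**What the test responds to here.** With most stays tied at one day, the test acts much like a comparison of the proportions kept longer. For 35% v 15% kept beyond day 1, the usual two-proportion approximation has null SE √(2×0.25×0.75/50) = 0.0866 and alternative SE √((0.35×0.65 + 0.15×0.85)/50) = 0.0843. Power is Φ[(0.20 − 1.96×0.0866)/0.0843] = Φ(0.36) ≈ 0.64, against 0.62 for Mann-Whitney in the matching 65/25/10 v 85/10/5 case. For 30% v 20% the figures are 0.21 and 0.22.

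**Stay in hours.** Common median 24 h and the same lower half; the excess above the median is exponential with mean 6 h in one arm and k h in the other. Here θ = 0.375 + 0.25k/(k + 6), and the mean difference is (k − 6)/2 hours.

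| k (h) | θ | Mean difference (h) | Rejects |
|---|---|---|---|
| 6 | 0.500 | 0 | 0.049 |
| 12 | 0.542 | 3 | 0.111 |
| 24 | 0.575 | 9 | 0.264 |
| 36 | 0.589 | 15 | 0.338 |

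**Equal medians, different spread only.** Lognormal with log-SD 0.3 v 0.6, 0.063; 0.3 v 0.9, 0.071; 0.3 v 1.0, 0.070. Normal with SD ratio 3, 0.069; ratio 5, 0.082.

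**Testing the medians directly.** A percentile-bootstrap 95% CI for the difference in medians (1,000 trials, 999 resamples) was run in four of the 1/2/3-day cases: 70/20/10 in both arms, 70/20/10 v 80/15/5, 65/25/10 v 85/10/5, and 60/25/15 v 90/8/2. It excluded zero in 0.0-0.1% of trials. In the three cases where the distributions differ, Mann-Whitney rejected in 22%, 62% and 96%.

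**The case against.** A reader might infer that the test has an inflated type I error, or that the trial would announce a difference in medians that does not exist. The documents support neither. Every scenario with a high rejection rate contains a real difference in stay. When the distributions are identical the test rejects at about 5%, so the high rates are power and only the label attached to the result is wrong. The plan also reports each arm's median with a CI, so a reader would usually see 1 v 1 day beside the P-value. That is confusing, but it exposes the mismatch.

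It is also fair to say that the tails are assumed. Followed literally, the day-1 instruction would leave almost no tail, and the rate then returns towards 5%. Stone size, named in the same clause, is fixed before randomization (the aim concerns "upper ureteric stones >10 mm" and impacted stones), so its distributions are equal by design. Describing the test as a comparison of medians is common shorthand. A test built for unequal distributions (Brunner-Munzel) rejects at nearly the same rates (0.66, 0.51 and 0.72 for 5% v 20%, 10% v 25% and 10% v 30%), so changing the test would alter little.

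All of this stands, and it limits the point to interpretation and reporting. It does not remove two facts: the stated target is not what the test addresses, and no between-arm estimate is planned to show what differs.

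**Conclusion.** The point holds as a minor one, for hospital stay only. The plan assigns the Mann-Whitney test to medians without the assumption that would justify it, and the shared discharge instruction makes equal medians with different upper tails plausible. With 50 per arm and 5-10% v 20-30% kept beyond day 1, about 50-72% of trials would give P < 0.05 with equal true medians. The rate depends heavily on the assumed shape: 11-34% in the hours model and about 6-8% when only spread differs. The documents give no data on stay with which to choose among these. The test itself is sound. Hospital stay is one of several aims, no primary endpoint is designated, and neither the sample size nor the comparison of stone-free rates depends on this clause.

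**What to change.** Replace the clause, for hospital stay, with wording such as: *The Mann-Whitney U test will compare the distributions of hospital stay between the groups. A significant result will not be described as a difference in medians. The between-group effect will be reported with a 95% CI as the difference in mean stay in days (bootstrap CI) and/or the probability that a Group A patient stays longer than a Group B patient, ties counted as half (Brunner-Munzel CI).*

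The mean difference has the advantage of being in days, which suits an aim that also covers cost. The probability measure matches the test but is less familiar to clinical readers. A bootstrap CI for the difference in medians is not a useful substitute: with heavy ties at day 1 it is nearly uninformative, as the check above shows.

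The cost is a change of wording and one extra estimate from data already collected, with no new patients or procedures. The section is written in the past tense; if the analysis has already been run, the same change applies to the report.

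### The planned Spearman correlations name no variable pairs and no handling of study group; the default single coefficient over both arms can mix a route effect with a patient-level relationship

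*Combined protocol and SAP*

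**What the plan says.** The Statistical analysis section, which follows the reference list, gives the correlations one sentence: "Spearman's correlation was used to analyze relationships between non-normally distributed variables". It lists no variables, pairs or purpose, and it does not mention study group. In the same paragraph, "the student's t-test was applied to compare means between study groups", and "the Mann-Whitney U test was used to compare medians for variables such as stone size and hospital stay". The section's only regression model is a logistic model for complications, which does not cover the correlations. All tests share one threshold: "A P-value < 0.05 was considered statistically significant".

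The Methodology section sets up two randomised arms: "Patients who fulfill inclusion criteria will be randomized into 2 groups", with "50 patients in either arm, aborted cases will be included". The Aim also undertakes to "evaluate feasibility, adverse events, hospital stay and cost benefit of both techniques". Correlation is not part of the stated aim.

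**The concern.** The trial is designed to detect differences between two routes. If route moves two outcomes, patients in one arm tend to sit higher (or lower) on both, and the pooled ranks correlate even when the outcomes are unrelated among patients treated by the same route. Judged at 0.05, that could be reported as a clinical relationship when it only restates the arm difference. If route moves the two outcomes in opposite directions, a genuine within-route relationship can be diluted or cancelled. Nothing in the documents stratifies or adjusts the correlations, so an analyst following the text would most likely compute one coefficient over 100 patients.

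**Working it through.** **Inputs from the documents.** 50 patients per arm (Methodology, Sample Size); significance at 0.05, with sidedness not stated (Statistical analysis). Two-sided testing is assumed. The documents have no figure for a correlation that could be reproduced.

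**Assumed inputs.** Route shifts d1 and d2, in within-arm SDs on the log scale, and the within-arm log-scale correlation rho. The documents give none of these, so a range is shown.

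**Formula.** For two equal arms, the pooled correlation on the log scale is

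r_pooled = (rho + d1·d2/4) / √[(1 + d1²/4)(1 + d2²/4)]

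- rho = 0, d1 = d2 = 0.5: 0.0625/1.0625 = 0.06
- rho = 0, d1 = d2 = 0.8: 0.16/1.16 = 0.14
- rho = 0, d1 = d2 = 1.0: 0.25/1.25 = 0.20
- rho = 0.3, shifts +0.5 and −0.5: (0.3 − 0.0625)/1.0625 = 0.22
- rho = 0.3, shifts +0.8 and −0.8: (0.3 − 0.16)/1.16 = 0.12
- rho = 0.3, shifts +1 and −1: (0.3 − 0.25)/1.25 = 0.04
- rho = 0.3, one variable shifted by 0.8: 0.3/√1.16 = 0.28

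**Simulation.** 20,000 trials per setting, 50 per arm, log-normal variables. The pooled Spearman test (n = 100) is compared with the average of the two within-arm Fisher-z values, with variance 1.06/47 per arm.

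| Within-arm rho | Shifts (SD) | Pooled mean r | Pooled P<0.05 | Within-arm P<0.05 |
|---|---|---|---|---|
| 0 | 0, 0 | 0.00 | 5.1% | 4.5% |
| 0 | 0.8, 0 | 0.00 | 4.9% | 4.3% |
| 0 | 0.3, 0.3 | 0.02 | 5.5% | 4.4% |
| 0 | 0.5, 0.5 | 0.06 | 8.5% | 4.4% |
| 0 | 0.8, 0.8 | 0.14 | 27.9% | 4.4% |
| 0 | 1.0, 1.0 | 0.20 | 53.1% | 4.3% |
| 0.3 | 0, 0 | 0.29 | 82.6% | 80.1% |
| 0.3 | 0.8, 0 | 0.26 | 76.8% | 80.6% |
| 0.3 | 0.5, −0.5 | 0.21 | 55.5% | 80.0% |
| 0.3 | 0.8, −0.8 | 0.10 | 17.7% | 80.1% |
| 0.3 | 1.0, −1.0 | 0.02 | 5.1% | 80.0% |

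Separate runs of the 1 SD same-direction setting gave 52% to 54%. A partial rank correlation adjusted for arm kept about 5% error and about 82% power in every setting.

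**Precision lost by combining arms.** The standard error on the Fisher-z scale is √(1.06/94) = 0.106 within arm, against √(1.06/97) = 0.105 pooled. The ratio is √(97/94) = 1.016, so the interval is about 1.6% wider.

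**The case against.** A reader might infer that the plan has decided to pool. The documents do not show that. Only the t-test clause mentions study groups explicitly, and the chi-square and Fisher sentences omit the group although they presumably compare the arms. The omission may be house style. What stands is that the text is silent and that an unadjusted coefficient is the default result of following it.

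The harm also needs two non-normal outcomes that are both moved by route, and the documents identify no such pair. The two variables named as examples, stone size and hospital stay, are not one, because stone size is fixed before randomisation. Hospital stay and cost is the obvious candidate pair, but cost probably includes stay, so the scenario with no within-arm relation fits it poorly; the documents do not define cost. Both groups share the same discharge step after the day-1 blood sample (Post operative), so nothing in the documents supports a large route effect on stay. Stay counted in days would also be heavily tied, unlike the simulated variables.

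Finally, if route shifts both outcomes, they really are associated across all treated patients. The excess rejections are errors only if the within-route relationship is the target, and the plan does not say which it wants. These points limit how much the issue matters. They do not supply the missing specification.

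**Conclusion.** The point holds as a minor one. The plan leaves pairs and group handling open, and its default can mislead for outcome–outcome pairs that both differ by route. The size depends entirely on assumed shifts: the false-positive rate is barely raised at 0.3 SD (5.5%) and modest at 0.5 SD (8.5%), but large from about 0.8 SD (28%). Masking needs opposite shifts, and the near-total loss of power occurs at about 1 SD.

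Two stronger readings are not supported. One is that any pooled correlation here would be spurious: with only one variable shifted, the false-positive rate stays at 4.9%. Such pairs are not wholly untouched, however, because power at rho 0.3 drops from about 82% to about 76% with a 0.8 SD shift in the other variable. The other is that the trial's main conclusions are at risk: the randomised between-arm comparisons do not use these correlations and do not change.

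**What to change.** In the Statistical analysis section:

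- Name the variable pairs to be correlated and the purpose of each.
- Report a partial Spearman correlation adjusted for arm, with a 95% CI. The alternative is the combined within-arm coefficient (average of the two Fisher-z values). Show the two arm-specific values beside it, because averaging assumes a common correlation in both arms.
- Label these correlations exploratory.

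The cost is a few lines of SAP wording and a short re-analysis of data already collected. The price when there is no route effect is about 2.5 points of power for the combined within-arm version (82.6% to 80.1% at rho 0.3), and essentially none for the partial correlation.
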